7.3.2.4. Main Estimand Analysis

Tumor assessments will be derived according to the IWG treatment response criteria for malignant lymphoma (Cheson et al 2007) by INV assessment. The estimand of PFS, with its 5 attributes and the strategies for addressing the defined intercurrent events, is presented in Table 8.

Table 8: Estimand of Progression-Free Survival

Estimand Attribute	Definition			
Treatment	Tafasitamab in combination with LEN administered for up to 12 cycles in total, after which participants can continue with tafasitamab as monotherapy.			
Population	All participants with R/R DLBCL as per eligibility criteria who received at least 1 dose of tafasitamab and 1 dose of LEN			
Variable	PFS			
Intercurrent events	Event	Strategy	Rationale (if needed)	
	No postbaseline response assessment or not adequately assessed (eg, NE)	Hypothetical strategy	Participants will be considered as having no event; early deaths will be considered as events (see Table 6)	
	Treatment discontinuation due to any reason	Treatment policy	All assessments will be considered regardless of treatment discontinuation	
	Death without adequate assessment	Composite strategy	Participant will be considered as having disease progression unless they have 2 consecutive missed assessments	
Death or progression after 2 or more missed assessments Hypothetical		Hypothetical strategy	Participants will be censored and only responses before missed assessments will be considered	
	Start of any NALT Hypothetical strategy Only the sta will b			
	Study withdrawal due to any reason	While on treatment strategy	All assessments will be considered up to study withdrawal	
Population-level summary	Kaplan-Meier estimate and 95% CI. The median PFS time and 95% CIs will be presented (Brookmeyer and Crowley 1982). The 25th and 75th percentiles will be reported.			

The PFS probabilities at specific timepoints (eg, 1, 3, 6, 12, 18, and 24 months) and the associated 95% CIs (Greenwood formula) will be summarized.

All PFS events will be described according to the type of event (death vs PD). The reasons for censoring will be tabulated.

A plot of the Kaplan-Meier curve for PFS will be provided. No formal hypothesis testing will be conducted. Analysis of PFS will be conducted on the FAS.

Listings on PFS events/censoring will be generated based on the FAS.

7.3.2.5. Sensitivity Analysis

The following sensitivity analyses for the PFS endpoint will be performed:

- A PFS event occurring after 2 or more missed assessments will be considered an event and back-dated to the date of the next scheduled assessment.
- The PPS will be used as a sensitivity analysis to the FAS.

7.3.3. Endpoint: Duration of Response

Duration of response is defined as the elapsed time between the date of first documented response (CR or PR) and the date of the first documented progression or death and will be calculated as

DoR (months) = (date of assessment of tumor progression or death – date of assessment of first documented response of CR or PR + 1) / 30.4375.

Only responders (ie, participants with PR or CR) will be considered in the analysis.

7.3.3.1. Censoring Rules

The censoring rules for DoR will be the same as those for PFS (see Table 6).

7.3.3.2. Analysis of Duration of Response

The distribution of DoR will be estimated using the Kaplan-Meier method. The median DoR and 95% CI will be presented as well as the 25th and 75th percentiles. A plot of the Kaplan-Meier curve for DoR will be provided. The DoR probabilities at specific timepoints (eg, 1, 3, 6, 12, 18, and 24 months) and the associated 95% CIs (Greenwood formula) will be summarized. A breakdown of events (death vs PD) and censoring reasons will be presented.

No formal hypothesis testing will be conducted. Analysis of DoR will be conducted on the FAS.

7.3.3.3. Sensitivity Analyses

The DoR endpoint will be analyzed using the PPS as a sensitivity analysis to the FAS.

7.3.3.4. Duration of Response for Participants With a Best Response of Complete Response

The DoR for participants with a best response of CR will be calculated as

DoR (months) = (date of assessment of tumor progression or death – date of assessment of first tumor response of CR + 1) / 30.4375.

The analysis of DoR as described in Section 7.3.3.2 will be performed based on the subset of participants in the FAS with a best response of CR.

7.3.4. Summary Statistics of Progression-Free Survival Follow-Up

Summary information regarding the follow-up of participants will be provided in order to describe the maturity of data and quality of follow-up for the efficacy analyses. The following will be presented for the FAS:

• Duration of follow-up time for PFS (months) = (date of event or censoring for PFS – study start reference date + 1) / 30.4375. Date of event or censoring is the same as defined in Section 7.3.2. This duration of follow-up will be estimated using a reverse Kaplan-Meier method to present the mean, 25th percentile, median, and 75th percentile. This will be reported based on the FAS, for the overall and recommended tafasitamab dose only.

9. PHARMACOKINETICS AND IMMUNOGENICITY

9.1. Analysis of Pharmacokinetics

Pharmacokinetic analyses will be conducted on the PKAS. Individual serum samples for the analysis of tafasitamab PK will be collected on various study days as per the schedule of assessments detailed in Section 2 of the Protocol.

Elapsed time will be calculated as

elapsed time from the first administration of tafasitamab (days) = date/time of assessment – date/time of the first administration of tafasitamab.

For samples collected 30 minutes after the end of the tafasitamab infusion, results will be excluded from summary statistics if the actual collection time is beyond \pm 15 minutes from the scheduled collection time. Such values will be flagged accordingly in the listing of PK data.

In the summary statistics and concentration-time profile graph, the value of BQL will be set to 0 for the Cycle 1 Day 1 predose assessment, to lower limit of quantification / 2 (25 ng/mL) for the first BQL value between 2 tafasitamab administrations or after the last tafasitamab administration, and will be treated as missing data in the assessments of other timepoints.

The tafasitamab serum concentration (μ g/mL) data will be summarized and plotted for each treatment group and/or cohort and overall using the PKAS. Detailed analyses will be presented as follows:

- Descriptive statistics of tafasitamab concentrations will be tabulated by visit and timepoint, including n, n-missing, arithmetic mean, geometric mean, STD, CV%, geometric CV%, median, minimum, and maximum.
- Serum concentration-time profiles with the mean \pm STD will be plotted across visit and timepoint. This will be performed on both the original serum concentration value and log serum concentration value.
- Listings of PK data will be generated to display the participant identifier, treatment group and/or cohort, visit, date/time of assessment, assessment timepoint, result, elapsed time, flag of collection time deviation, and reason for missing assessment. The concentration data will be presented with a maximum of 3 decimals.

9.2. Immunogenicity Analysis

Serum samples for the assessment of anti-tafasitamab antibodies will be collected as per the schedule of assessments detailed in Section 2 of the Protocol. In order to determine a participant's anti-tafasitamab antibody status, as a first step, a screening assay will be performed. Then, all screened positive samples will be tested again in a confirmatory assay. For all confirmed positive samples, the following additional assays will be performed: a semiquantitative ADA titer will be determined, the specificity toward MOR00208-hIgG1 or MOR00208-hIgG1/2a will be determined, and an nAb will be performed.

Anti-tafasitamab antibody samples will be defined as negative if they are screened or confirmed negative. Anti-tafasitamab antibody samples will be defined as positive if they are positive in

both the screening and the confirmatory assays. For all positive samples, an anti-tafasitamab antibody titer will be determined.

The immunogenicity data will be summarized for each treatment group and/or cohort and overall, using the IAS, as follows:

- Summary of the anti-tafasitamab antibody status; the number and percentage of participants will be tabulated to present the following categories:
 - Participants with pre-existing anti-tafasitamab antibodies (ie, participants who are positive for anti-tafasitamab antibodies on Cycle 1 Day 1).
 - Participants without anti-tafasitamab antibodies after treatment initiation (ie, participants who are negative for anti-tafasitamab antibodies on all occasions after Cycle 1 Day 1, irrespective of the baseline result).
 - Participants with anti-tafasitamab antibodies after treatment initiation (ie, participants who are positive for anti-tafasitamab antibodies on any occasion after Cycle 1 Day 1).
 - Participants with treatment-induced anti-tafasitamab antibodies (ie, participants who are negative for anti-tafasitamab antibodies on Cycle 1 Day 1 and positive on any other occasion).
 - Participants with treatment-boosted anti-tafasitamab antibodies (ie, participants who are positive for anti-tafasitamab antibodies on Cycle 1 Day 1 and who developed an increased titer on any other occasion).
- Summary of anti-tafasitamab antibody response per visit; the following will be tabulated:
 - Total number of participants
 - Number and percentage positive
 - Number and percentage negative
 - Number and percentage missing
- Summary of anti-tafasitamab antibody titer per visit; the following will be tabulated:
 - Number of participants with determined titers
 - o Number and percentage of neutralizing anti-tafasitamab antibodies
 - o Titers (summary statistics)
 - Number and percentage missing

In addition, listings of the immunogenicity data will be generated to display the participant identifier, treatment group, visit, date/time of assessment, assessment timepoint, type of assay (including specificity and nAb assay), result, and reason for missing assessment.

10. SAFETY AND TOLERABILITY

Appendix A provides a list of data displays. Sample data displays are included in a separate document.

10.1. General Considerations

Summary tables may be replaced with listings when appropriate. For instance, an AE frequency table may be replaced with a listing if it only contains a few unique PTs reported on relatively few participants.

10.2. Adverse Events

10.2.1. Adverse Event Definitions

10.2.1.1. Adverse Event

An AE is defined as any untoward medical occurrence in a participant temporally associated with the use of study treatment, whether or not considered related to the study treatment. Therefore, an AE can be any unfavorable or unintended sign (including an abnormal laboratory finding) or symptom temporally associated with the use of study treatment. As per Protocol, any abnormal safety assessment that qualifies as an AE (eg, laboratory abnormalities, ECG abnormalities) will be documented in the eCRF as an AE. From a programming aspect, no additional derivation of AE entries will be applied.

10.2.1.2. Adverse Event Prior to Study Treatment (Pretreatment Adverse Event)

Any AE that started prior to the date of first administration of study treatment and does not increase in severity after study treatment will be classified as a pretreatment AE.

10.2.1.3. Treatment-Emergent Adverse Event

A TEAE is defined as any AE that starts or worsens after the first dose of study treatment until 90 days after the last dose of the study treatment. An AE that was present prior to study drug administration but increased in severity after treatment start will also be included as a TEAE.

Events with missing onset dates will be included as a TEAE if the end date is not before the first dose of study treatment.

If the start date and time of an AE are partially or completely missing, the AE will be assumed to be a TEAE if it cannot be proven that the AE did not occur or worsen during the treatment period (worst-case approach).

Any missing onset date of a TEAE will be handled according the following rules:

- If completely missing, then Day 1 will be used.
- If only the day is missing, then the first day of the month or Day 1, whichever is later, will be used.
- If both the month and day are missing, then 01 JAN of the year or Day 1, whichever is later, will be used.

10.2.1.4. Adverse Events After the Safety Follow-Up Period

If an AE occurs more than 90 days after the end of treatment, it will be defined as an AE after the safety follow-up period.

10.2.1.5. Predefined Safety Events

The following are predefined safety events according to CTCAE v5 for the safety observation window (35 days from Cycle 1 Day 1):

- Grade 4 or higher nonhematologic AE
- Grade 4 or higher neutropenia (PTs: neutropenia and neutrophil count decreased) lasting > 7 days despite standard of care treatments (eg, G-CSF)
- Grade 4 or higher anemia
- Grade 3 or higher neutropenia (PTs: neutropenia and neutrophil count decreased) with associated fever (> 38.3°C) lasting > 7 days despite standard of care treatments (eg, anti-infectives, G-CSF)
- Grade 3 or higher IRR (as per eCRF)
- Grade 3 or higher TLS (PT: tumour lysis syndrome)
- Grade 3 or higher thrombocytopenia (PTs: platelet count decreased and thrombocytopenia) with clinically significant bleeding
- Grade 2 or higher CRS (PTs: cytokine release syndrome and cytokine storm)

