## 5.2 Data and Safety Monitoring Committee

A data and safety monitoring committee (DSMC), consisting of Sponsor representatives and investigators, will continuously monitor the study and can recommend to stop enrollment at any time based on emerging safety data and pre-defined stopping rules. In addition, pre-defined DSMC meetings will take place when 6 patients have completed the 5-week safety observation period (35 days from C1D1 onwards) [REDACTED] respectively.

Details of specific responsibilities, composition, meeting formats and frequency of the DSMC are outlined in the Data Safety Monitoring Committee Charter.

A recommendation [REDACTED]  
[REDACTED]  
[REDACTED]  
[REDACTED]  
[REDACTED]

The DSMC recommendations will be guided by pre-defined safety criteria that apply to the safety observation window of 35 days (from Cycle 1 Day 1 to Cycle 2 Day 7).

Pre-defined safety criteria (stopping rules):

- [REDACTED]
- [REDACTED]
- [REDACTED]

The pre-defined safety events are the following according to CTCAE version 5:

- Grade 4 or higher non-hematologic AE
- Grade 4 or higher neutropenia lasting > 7 days, despite standard of care treatments (i.e. G-CSF, others as needed)
- Grade 4 or higher anemia
- Grade 3 or higher neutropenia with associated fever (> 38.3 °C) lasting > 7 days, despite standard of care treatments (i.e. anti-infectives, G-CSF, others as needed)
- Grade 3 or higher IRR
- Grade 3 or higher TLS
- Grade 3 or higher thrombocytopenia with clinically significant bleeding
- CRS Grade 2 or higher

Events that are clearly attributed to the underlying disease or LEN alone will be discussed at the DSMC and a decision will be made whether these events should be considered as a pre-defined safety event.

If the safety results [REDACTED]  
[REDACTED]  
[REDACTED] in approximately 45 patients in total.

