**Table 14: Hematological Toxicities**

Hematological Toxicity	LEN 	Tafasitamab
Neutropenia Grade 4 (ANC < 500/μl) with or without a temperature of ≥ 38.0°C/100.4°F	Interrupt LEN.	Withhold tafasitamab infusion.
	If neutropenia has resolved to ≤ Grade 2 (ANC ≥ 1,000/μl) within 7 days, LEN should be restarted in the next cycle at the same dose. If neutropenia has not resolved to ≤ Grade 2 within 7 days, LEN should be resumed in the next cycle at the next lower dose level (see Table 13 above). Monitor CBC at least QW until neutrophil count is ≥ 1,000/μl.	If neutropenia has resolved to ≤ Grade 2, resume tafasitamab. Monitor CBC at least QW until neutrophil count is ≥ 1,000/μl.
Neutropenia Grade 3 (ANC < 1,000/μl) > 7 days	LEN should be resumed in the next cycle at the next lower dose level (see Table 13 above).	Hold tafasitamab until resolved to ≤ Grade 2 (ANC ≥ 1,000/μl).
Neutropenia Grade 3 (ANC < 1,000/μl) with a temperature of ≥ 38.0°C/100.4°F (Febrile Neutropenia)	Interrupt LEN.	Interrupt tafasitamab.
	If infection is resolving (< 38°C/100.4°F), and neutropenia has resolved to ≤ Grade 2, LEN should be resumed in next cycle at the next lower dose level (see Table 13 above).	If infection is resolving (< 38°C/100.4°F), continue tafasitamab as per protocol.
Neutropenia < Grade 3 associated with infection ≥ Grade 3 or fever (≥ 38.0°C body temperature)	First occurrence interrupt LEN.	Interrupt tafasitamab.
	If infection is resolving (< 38°C/100.4°F), LEN should be restarted in the next cycle at the same dose.	If infection is resolving (< 38°C/100.4°F), continue tafasitamab per protocol.
	Re-occurrence: interrupt LEN. If infection is resolving (< 38°C/100.4°F), LEN should be restarted in the next cycle at the next lower dose level.	
Thrombocytopenia Grade 3-4 (PLT < 50,000/μl) with or without bleeding	Interrupt VTE prophylaxis.	
	Consider platelet transfusion according to institutional guidelines. If thrombocytopenia has resolved to ≤ grade 1, consider change of VTE prophylaxis agent (e.g. change antiplatelet agent to low molecular weight heparin). VTE prophylaxis should be tailored to the patient's individual risk/benefit profile by taking into account the individual thrombotic risk and bleeding risk.	

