**12.12.3 Recording and Follow-Up of AE and/or SAE**

AE and SAE Recording

 
• When an AE/SAE occurs, it is the responsibility of the investigator to review all documentation (e.g., hospital progress notes, laboratory reports, and diagnostics reports) related to the event
 
• The investigator will then record all relevant AE/SAE information in the eCRF
 
• It is not acceptable for the investigator to send photocopies of the patient's medical records to the sponsor in lieu of completion of the sponsor/AE/SAE CRF page
 
• There may be instances when copies of medical records for certain cases are requested by the sponsor. In this case, all patient identifiers, except for the patient number, will be redacted on the copies of the medical records before submission to the sponsor
 
• The investigator will attempt to establish a diagnosis of the event based on signs, symptoms, and/or other clinical information. Whenever possible, the diagnosis (not the individual signs/symptoms) will be documented as the AE/SAE.
 

Assessment of Intensity

The investigator will assess the intensity for each AE and SAE reported during the study and assign it to one of the following categories:
 
 
• Mild: An event that is easily tolerated by the patient, causing minimal discomfort and not interfering with everyday activities
 
• Moderate: An event that causes sufficiently discomfort and interferes with normal everyday activities
 
• Severe: An event that prevents normal everyday activities. An AE that is assessed as severe should not be confused with a SAE. Severe is a category utilized for rating the intensity of an event; and both AEs and SAEs can be assessed as severe
 
 
An event is defined as 'serious' when it meets at least 1 of the predefined criteria as described in the definition of an SAE, NOT when it is rated as severe.

Assessment of Severity (toxicity grade)

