10.2.1.6. Hematological Adverse Events

Hematological AEs will belong to the following 4 categories: neutropenia, febrile neutropenia, anemia, thrombocytopenia. The 4 categories include the following PTs:

- PTs used to identify neutropenia: neutropenia and neutrophil count decreased
- PTs used to identify anemia: anemia and red blood cell count decreased
- PTs used to identify thrombocytopenia: platelet count decreased and thrombocytopenia
- PT used to identify febrile neutropenia: febrile neutropenia

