10.2.5. Adverse Event and Death Listings

All AEs/TEAEs will be listed by cohort and treatment group and sorted by participant identification number along with the start date (day) and end date (day), duration, if serious, if an AESI, if related to tafasitamab/LEN, toxicity grade (highest), action taken with tafasitamab/LEN, other actions taken, tafasitamab start/end dates, LEN start/end dates, outcome, earliest date participant received prohibited concomitant medication (if applicable), and a flag to evaluate whether predefined safety event criteria are met. Listings will be generated for the ENR, with inclusion in the SAF and PAS noted, for the following:

- All AEs recorded throughout the study to show all information captured in the "Adverse Event" eCRF. The listing will include a flag to evaluate if the AE meets the predefined safety events criteria.
- All infusion-related AEs recorded throughout the study to show all information captured in the "Adverse Event" eCRF.
- All SAEs recorded throughout the study to show all information captured in the "Adverse Event" eCRF, including criteria for SAE met.
- All AESIs recorded throughout the study to show all information captured in the "Adverse Event" eCRF, including criteria for AESI met.
- All AEs with an onset date after the start date of prohibited concomitant medication.

All deaths, with an indicator if death occurred pretreatment, on treatment, or post-treatment, will be listed by cohort and treatment group and sorted by participant identification number along with the date of death (day) and cause of death, tafasitamab start/end dates, LEN start/end dates, and if applicable, earliest date participant received prohibited concomitant medication. The listing will be generated for the ENR, with inclusion in the SAF and PAS noted, and will include all assessments/events and a flag for those that are pre- and post-treatment assessments/events.

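### The SAP's febrile-neutropenia safety criterion leaves out the preferred term febrile neutropenia, so a qualifying event recorded only under that term is not flagged

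*SAP*

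**What the plan says.** Protocol 5.2 lists the predefined safety events that guide the Data and Safety Monitoring Committee (DSMC) over the 35 days from Cycle 1 Day 1. One is "Grade 3 or higher neutropenia with associated fever", with fever defined as above 38.3 °C, lasting more than 7 days despite standard of care. It names no preferred term (PT).

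SAP 10.2.1.5 turns the list into an analysis definition. There the item becomes "Grade 3 or higher neutropenia (PTs: neutropenia and neutrophil count decreased) with associated fever", with the same temperature, duration and standard-of-care conditions.

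SAP 10.2.1.6 gives the same two PTs for neutropenia and adds a further line: "PT used to identify febrile neutropenia: febrile neutropenia". It also states: "Hematological AEs will belong to the following 4 categories: neutropenia, febrile neutropenia, anemia, thrombocytopenia".

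The definition is used in SAP 10.2.5, for the listing of all adverse events (AEs): "The listing will include a flag to evaluate if the AE meets the predefined safety events criteria". SAP 10.2.1.1 says of AE records: "From a programming aspect, no additional derivation of AE entries will be applied".

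On recording, Protocol 12.12.3 instructs sites: "Whenever possible, the diagnosis (not the individual signs/symptoms) will be documented as the AE/SAE". The Grade 3 fever row of Protocol Table 14 carries a diagnostic label of its own: "with a temperature of ≥ 38.0°C/100.4°F (Febrile Neutropenia").

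**The concern.** The PT that names neutropenia with fever is missing from the SAP's only criterion for neutropenia with fever. The two listed PTs cannot be read as covering it, because the next SAP section treats it as a separate PT.

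Recording such an event only as febrile neutropenia is plausible. Sites are asked to enter the diagnosis rather than its components, and the protocol itself uses that diagnosis as a label. Two patients with the same clinical course could then receive different flags because their sites chose different, equally valid terms.

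At stake is the accuracy of a listing flag meant to reproduce a protocol criterion. That criterion covers the observation window behind the DSMC's recommendations, in a study whose primary objectives include a recommended dose.

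**Working it through.** The plan gives no figure to reproduce. The check applies the rules as written.

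**Step 1: does any SAP criterion catch the event?** Take an event in the 35-day window recorded only as febrile neutropenia, at 38.5 °C, for 10 days, despite standard of care. At Grade 3 or Grade 4 it meets the febrile criterion of Protocol 5.2. Against the eight items of SAP 10.2.1.5:

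| SAP item | Met? | Reason |
|---|---|---|
| 1. Nonhematologic, Grade 4+ | No | SAP 10.2.1.6 classes febrile neutropenia as hematological |
| 2. Prolonged neutropenia, Grade 4+ | No | Same two PTs only |
| 3. Anemia, Grade 4+ | No | Different event |
| 4. Neutropenia with fever, Grade 3+ | No | Two PTs only; febrile neutropenia not listed |
| 5. Infusion-related reaction, Grade 3+ | No | Different event |
| 6. Tumor lysis syndrome, Grade 3+ | No | Different event |
| 7. Thrombocytopenia with bleeding, Grade 3+ | No | Different event |
| 8. Cytokine release syndrome, Grade 2+ | No | Different event |

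The result is 0 of 8 at Grade 3 and 0 of 8 at Grade 4. Under SAP 10.2.1.1, a neutropenia AE is not created by programming from the blood counts.

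**Step 2: does the outcome depend on the term entered?** Assumed Grade 3 test cases: temperature 38.1 or 38.5 °C, duration 5 or 10 days, despite standard of care yes or no, so 2 × 2 × 2 = 8 cases. Only one (38.5 °C, 10 days, yes) meets the protocol criterion. The other 8 − 1 = 7 do not.

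| Rule and recorded term | Qualifying case flagged | Other cases flagged |
|---|---|---|
| As written, febrile neutropenia only | 0 of 1 | 0 of 7 |
| As written, neutropenia only | 1 of 1 | 0 of 7 |
| As written, neutrophil count decreased only | 1 of 1 | 0 of 7 |
| As written, febrile neutropenia plus neutropenia | 1 of 1 | 0 of 7 |
| PT added, all conditions checked, any of these four routes | 1 of 1 | 0 of 7 |
| PT taken as proof of the conditions, febrile neutropenia only | 1 of 1 | 7 of 7 |

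This tests the rule and estimates no frequency; the counts follow from the chosen grid. It shows that the flag depends on the term, that adding the PT removes the dependence, and that the PT must not replace the conditions. Protocol Table 14 applies its label from 38.0 °C, below the 38.3 °C of Protocol 5.2.

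**Step 3: how often?** The documents do not allow a count. Protocol Table 7 reports febrile neutropenia as its own term in 5 of 81 L-MIND patients (5/81 = 6.2%). Those are tafasitamab-related events of any grade over the whole treatment. The figure shows that the term is used. It does not show how often it appears without a neutropenia AE, or how many events would meet the fever, duration and window conditions.

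**The case against.** The strongest case on the other side is that the practical effect is small and may not arise at all.

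- **Limited use.** The definition feeds a listing flag. Appendix A plans no table or figure of predefined safety events. Febrile neutropenia still appears in the tables of treatment-emergent AEs (TEAEs) of Grade 3 or higher, and has its own time-to-onset summary. SAP 3.5.1 refers the DSMC criteria back to Protocol 5.2, and Protocol 10.3.1 gives the DSMC patient profiles and AE listings. All of this stands, and nothing in the documents shows that a stopping recommendation would be missed.
- **Co-reporting.** Protocol 9.4.5 requires clinically significant laboratory changes to be entered as AEs, and Protocol 12.12.1 counts such results as AEs. A Grade 3 count lasting more than 7 days would often qualify, and a qualifying neutropenia record closes the gap. This stands as a mitigation. It does not remove the gap, because Protocol 12.12.3 pulls the other way by preferring the diagnosis.
- **Case review.** Fever above 38.3 °C and failure of standard care cannot be read from a PT, so someone must look at each case and could flag the event anyway. That is possible, but the SAP does not say that the flag is assigned by medical review regardless of PT. A reader who follows the text would apply the PT list.
- **SAP 10.2.1.1.** The sentence on derivation concerns creating AE records and does not govern how the flag is assigned. That is a fair reading. It matters here only because no neutropenia record will be generated to rescue the event.

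**Conclusion.** The concern holds. As written, SAP 10.2.1.5 is narrower than Protocol 5.2: an event recorded only as febrile neutropenia that meets every protocol condition satisfies 0 of the 8 SAP criteria and is not flagged. Confidence in the mismatch is high, because it follows directly from the text.

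The conclusion rests on two assumptions: that the event has no accompanying qualifying record of neutropenia or neutrophil count decreased, and that the flag is assigned by the PT list as stated. The number of affected events is unknown. The primary endpoint and the TEAE tables are unaffected. The point should be fixed because the flag contradicts the criterion it is meant to reproduce and the correction is very small.

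**What to change.** In SAP 10.2.1.5, add febrile neutropenia to the PT list of the criterion for neutropenia of Grade 3 or higher with fever. Add a clause stating that the grade, the temperature above 38.3 °C, the duration above 7 days and the standard-of-care condition are verified for each event, whichever PT is recorded, so that the PT alone never sets the flag.

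The cost is one term and half a sentence. No new data are needed, and the clinical criteria in Protocol 5.2 stay as they are.
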